## 10.2 Secondary Outcome Measures

**The number (proportion) of lymph nodes determined to be tumor-positive by histological and/or pathological evaluation that were NOT predicted tumor-positive by Zr-panitumumab labeling.**

We will compare the number and location of F-FDG-avid nodes within the regional lymphatics to the number and location of Zr-panitumumab-avid nodes in relation to the postoperative neck dissection histopathology (gold standard).

**Outcome Measure:** Preoperatively, the location and number of F-FDG-avid nodes as well as the number and location of Zr-panitumumab-avid nodes will be determined. Once all radioactive and fluorescent nodes are removed intraoperatively, standard of care will be performed via completion neck dissection. The excised tissue specimens will be sent to pathology where the tumor status of the lymph nodes will be determined (histology serves as our gold standard). This will allow us to determine true and false positive and negative tumor values for Zr-panitumumab and F-FDG in identifying the tumor-loaded lymph nodes. Specifically we will look for lymph nodes that were F-FDG positive on preoperative imaging and/or fluorescently labeled by panitumumab-IRDye800, but do not show uptake of Zr-panitumumab.

**Time Frame:** Final false positive and negative rate, sensitivity and specificity of sentinel node detection using panitumumab-IRDye800 can be determined towards the completion of the trial (once all subjects have been included and all the data have been collected).

**Safety Issue:** No

## 11. REGULATORY REQUIREMENTS

### 11.1 Institutional Review of Protocol

The protocol, the proposed informed consent and all forms of participant information related to the study (e.g. advertisements used to recruit participants) will be reviewed and approved by the Stanford IRB and Stanford Cancer Institute Scientific Review Committee (SRC). Any changes made to the protocol will be submitted as a modification and will be approved by the IRB prior to implementation. The Protocol Director will disseminate the protocol amendment information to all participating investigators. The protocol and any significant amendments will be submitted to FDA.

### 11.2 Data and Safety Monitoring Plan

The Stanford Cancer Institute Data and Safety Monitoring Committee (DSMC) will be the monitoring entity for this study. The DSMC will audit study-related activities to determine whether the study has been conducted in accordance with the protocol, local standard operating procedures, FDA regulations, and Good Clinical Practice (GCP). This may include annual review of the following types of documents participating in the study: regulatory binders, case report forms, eligibility checklists, and source documents. In addition, the DSMC will regularly (monthly) review any DLTs, serious adverse events, and protocol deviations associated with the research to ensure the protection of human subjects. Results of

the DSMC audit will be communicated to the IRB and the appropriate regulatory authorities at the time of continuing review, or in an expedited fashion, as needed.

### **11.3 Data Management Plan**

The Protocol Director, or designees noted in the Delegation of Authority Log, will maintain adequate and accurate participant case histories with observations and other data pertinent to the study. Original source documents will be transcribed to Case Report Forms (CRFs). Source documents include hospital records, clinical charts, laboratory and pharmacy records, and recorded electronic data. Case report forms will be developed using the OnCore database system and maintained by the study team. CRFs will be kept in a locked office, only accessible to the research team.

## **12. STATISTICAL CONSIDERATIONS**

Data from both cohorts (14 subjects) will be combined for all primary and secondary analyses.

### **Primary objective**

**Determine the sensitivity and specificity of Zr-panitumumab for the detection of tumor-involved regional lymph nodes.**

Using the histological and/or pathological evaluation of the lymph node as the gold standard, we will calculate and compare the sensitivity and specificity of Zr-panitumumab and F-FDG PET/CT imaging findings. We will test the level of association of the Zr-panitumumab-PET results and the F-FDG-PET results with the Phi coefficient.

We will use the matched pair Durkalski's test (36), accounting for the cluster-correlation within subjects, for the sensitivity and specificity comparisons (primary and exploratory) using the clust.bin.pair package (37) in the R-statistical software (39). Significance for both primary and exploratory analyses will be assessed at the 0.05 level and to assess uncertainty, 95% confidence intervals will be provided for all estimates.

### **Secondary Objective**

**Determine the number (proportion) of lymph nodes determined to be tumor-positive by histological and/or pathological evaluation that were NOT predicted tumor-positive by Zr-panitumumab labeling.**

We will calculate the odds of a false negative using Zr-panitumumab-PET relative to the odds of a false negative using a F-FDG-PET and compare the negative predictive value (NPV) of Zr-panitumumab and F-FDG.

### **Exploratory Objectives**

- **Determine the sensitivity and specificity of panitumumab-IRDye800 for the detection of tumor-involved regional lymph nodes.**
- After isolation of lymph nodes from the specimen in the pathology lab, lymph node fluorescence will be measured prior to histological and/or pathological evaluation (gold standard). Sensitivity and specificity will be generated by comparison of fluorescence intensity and histological and/or pathological evaluation (gold standard). Findings will furthermore be compared to the sensitivity and specificity of Zr-panitumumab and F-FDG (primary objective) using Durkalski's test, as outlined above.

- Determine the number (proportion) of lymph nodes determined to be tumor-positive by histological and/or pathological evaluation that were NOT predicted tumor-positive by panitumumab-IRDye800 labeling.
- We will determine the level of association between panitumumab-IRDye800 results and  $^{89}\text{Zr}$ -panitumumab-PET and  $^{18}\text{F}$ -FDG-PET results with the Phi coefficient.

Descriptive statistics

For qualification and quantification of the fluorescence signal and the radioactive signal, we follow the following rules:

- *Intraoperative fluorescence assessment of panitumumab-IRDye800:*  
There will be no set level of fluorescence whereby we consider tissue positive or negative; it is based on operator's impression.
- *Ex vivo fluorescence assessment of panitumumab-IRDye800:*  
From the fluorescence images taken in the operation room, we will calculate tumor-to-background ratios (TBRs) as such to define a more quantitative read-out (similar to as described in the IRB-35064 study). Based on the current data available from our IRB-35064, in our 50 mg cohort, we found an average TBR of  $6.53 \pm 1.2$ , a sensitivity of  $89 \pm 5.1\%$ , a specificity of  $92 \pm 3.5\%$  (AUC:  $0.93 \pm 0.05$ ). The NPV and PPV were  $94 \pm 2.8\%$  and  $92 \pm 9.5\%$ , respectively. We will extrapolate these findings to the current study to further validate the findings from our phase I study (IRB-35064).
- *Radioactive assessment of  $^{89}\text{Zr}$ -panitumumab:*  
Following the standard of care evaluation of PET/CT scans, maximum standard uptake values ( $\text{SUV}_{\text{max}}$ ) will be calculated for the accumulation of  $^{89}\text{Zr}$ -panitumumab in tumor tissue and/or lymph nodes. As background reading, the  $\text{SUV}_{\text{max}}$  of the mediastinum will be determined.  
Tentative cutoff for 'imaging positive': an  $\text{SUV}_{\text{max}}$  value of the lymph nodes of minimally  $1.4 \times$  the background (mediastinum). In all cases, (histo-) pathology serves as the gold standard for "true" positive / negative lymph nodes. Subsequently an ROC curve will be generated whereby we will select the point of highest specificity and sensitivity and from there we will determine if our tentative cutoff was valid or if we need to adjust.
- *Comparison fluorescence and radioactivity-based findings:*  
All tissues that will be excised during surgery will be evaluated for the presence of radioactivity and fluorescence and scored as such being positive / negative. Evaluated tissues are either 1) fluorescent only; 2) radioactive only; 3) both radioactive and fluorescent; or 4) neither radioactive nor fluorescent. This will be done quantitatively (Y/N approach) and qualitatively (see above).
  - Because the antibody is the same, only the label (IRDye800 or  $^{89}\text{Zr}$ ) differs, we expect that tissue samples that are radioactive are also fluorescent and vice versa. However, this is something that will be investigated in this study.

We will present means and standard deviations (or medians and interquartile ranges when appropriate) for continuous characteristics such as maximum standard uptake values ( $\text{SUV}_{\text{max}}$ ) as determined with  $^{89}\text{Zr}$ -panitumumab-PET and  $^{18}\text{F}$ -FDG-PET and radioactivity counts of  $^{89}\text{Zr}$ -panitumumab in the node(s) as determined with the beta probe and/or high-energy gamma probe, and tumor-to-background ratios (TBRs) and mean fluorescence intensity (MFI) for panitumumab-IRDye800. For categorical variables such as drainage pattern and number of lymph nodes visualized, we will present frequency statistics. Graphical tools such as heat maps, histograms, and boxplots will be used to assess distributional properties of continuous variables. We will illustrate the nature of the relationship between  $\text{SUV}_{\text{max}}$ /radioactivity counts and/or MFI/TBRs and/or drainage pattern across all subjects, the relationship will be illustrated with a heat map and spaghetti plot. When appropriate, transformations – including a log-based transformation – may be considered to stabilize variance

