**Outcome measures to answer the primary and secondary objectives set:**

Preoperative data:

1. Collect safety data on tracer-infusion.
2. The number and location of F-FDG-PET positive nodes.
3. The number and location of Zr-panitumumab-PET positive nodes.

Intraoperative data:

4. The number and location of Zr-panitumumab-PET positive nodes.
5. The number and location of panitumumab-IRDye800 positive nodes.

Post-operative data:

6. Collect safety data in follow-up (up to 30 days post-infusion).
  - a. This includes tests and observations to identify both acute and late-treatment specific toxicity: vital signs; physical exam; toxicity grading; assignment of performance status; hematology; and blood chemistries (basic metabolic profile to include magnesium and phosphorus). NCI Common Toxicity Criteria v5.0 will be used for grading of toxicity.
7. Determine *ex vivo* fluorescence imaging information on panitumumab-IRDye800 (method described previously in (21)).
8. Determine the histo-pathological status of the primary tumor.
9. Determine the histo-pathological status of the lymph nodes: tumor-positive (isolated tumor cells, micro- or macro-metastasis) or tumor-negative.
10. Determine, using immunohistochemistry, on the surgically excised tissue specimens:
  - a. Tumor tissue viability
  - b. EGFR expression
  - c. Vessel density

We have previously described the methods for analysis in (26).

For qualification and quantification of the fluorescence signal and the radioactive signal, we follow the following rules:

- *Intraoperative fluorescence assessment of panitumumab-IRDye800:*

There will be no set level of fluorescence whereby we consider tissue positive or negative; it is based on operator's impression.

- *Ex vivo fluorescence assessment of panitumumab-IRDye800:*

From the fluorescence images taken in the operation room, we will calculate tumor-to-background ratios (TBRs) as such to define a more quantitative read-out (similar to as described in the IRB-35064 study). Based on the current data available from our IRB-35064, in our 50 mg cohort, we found an average TBR of  $6.53 \pm 1.2$ , a sensitivity of  $89 \pm 5.1\%$ , a specificity of  $92 \pm 3.5\%$  (AUC:  $0.93 \pm 0.05$ ). The NPV and PPV were  $94 \pm 2.8\%$  and  $92 \pm 9.5\%$ , respectively. We will extrapolate these findings to the current study to further validate the findings from our phase I study (IRB-35064).

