- *Radioactive assessment of Zr-panitumumab:*

Following the standard of care evaluation of PET/CT scans, maximum standard uptake values ( $SUV_{max}$ ) will be calculated for the accumulation of Zr-panitumumab in tumor tissue and/or lymph nodes. As background reading, the  $SUV_{max}$  of the mediastinum will be determined.

Tentative cutoff for 'imaging positive': an  $SUV_{max}$  value of the lymph nodes of minimally  $1.4 \times$  the background (mediastinum). In all cases, (histo-) pathology serves as the gold standard for "true" positive / negative lymph nodes. Subsequently a ROC curve will be generated whereby we will select

the point of highest specificity and sensitivity and from there we will determine if our tentative cutoff was valid or if we need to adjust.

- *Comparison fluorescence and radioactivity-based findings:*

All tissues that will be excised during surgery will be evaluated for the presence of radioactivity and fluorescence and scored as such being positive / negative. Evaluated tissues are either 1) fluorescent only; 2) radioactive only; 3) both radioactive and fluorescent; or 4) neither radioactive nor fluorescent. This will be done quantitatively (Y/N approach) and qualitatively (see above).

- Because the antibody is the same, only the label (IRDye800 or 89-Zr) differs, we expect that tissue samples that are radioactive are also fluorescent and vice versa. However, this is something that will be investigated in this study.

Statistical considerations are described in detail in Section 11.

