## **10. MEASUREMENTS**

### **10.1 Primary Outcome Measure**

**The number (proportion) of lymph nodes determined to be tumor-positive by histological and/or pathological evaluation that were predicted to be tumor-positive by  $^{89}\text{Zr}$ -panitumumab labeling.**

We will compare the number and location of  $^{18}\text{F}$ -FDG-avid nodes within the regional lymphatics to the number and location of  $^{89}\text{Zr}$ -panitumumab-avid nodes in relation to the postoperative neck dissection histopathology (gold standard).

**Outcome Measure:** Preoperatively, the location and number of  $^{18}\text{F}$ -FDG-avid nodes as well as the number and location of  $^{89}\text{Zr}$ -panitumumab-avid nodes will be determined by 2 board-certified Nuclear Medicine physicians ([name] and [name]). Once all radioactive and fluorescent nodes are removed intraoperatively, standard of care will be

performed via completion neck dissection. The excised tissue specimens will be sent to pathology where the tumor status of the lymph nodes will be determined (histology serves as our gold standard). This will allow us to determine true and false positive and negative tumor values for Zr-panitumumab and F-FDG in identifying the tumor-loaded lymph nodes.

**Time Frame:** Final false positive and negative rate, sensitivity and specificity of sentinel node detection using Zr-panitumumab can be determined towards the completion of the trials (once all subjects have been included and all the data has been collected).

**Safety Issue:** No

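### The plan does not say which 89Zr positivity rule governs the primary and secondary results once the tentative cut-off has been through an ROC step on the same nodes

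*Combined protocol and SAP*

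**What the plan says.** Section 2.4 (radioactive assessment of 89Zr-panitumumab) and Section 12 (Descriptive statistics) carry the same rule. A node is imaging-positive if its SUVmax is at least 1.4 times the mediastinal SUVmax, and this cut-off is called tentative. Pathology is the reference standard. Section 12 continues: "an ROC curve will be generated whereby we will select the point of highest specificity and sensitivity". The purpose is given in Section 2.4: "we will determine if our tentative cutoff was valid or if we need to adjust". In Section 2.4 this text belongs to the outcome measures for the primary and secondary objectives. In Section 12 it follows the exploratory objectives.

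Other places describe the 89Zr result as a call made before surgery:
- The synopsis compares pathology with nodes that looked suspicious on imaging.
- The registry text in Section 2.4 defines the primary outcome as pathology-positive nodes that the 89Zr scan had predicted.
- The outcome list in Section 2.4 puts the number and location of PET-positive nodes under "Preoperative data".
- Section 10.1 says that, before surgery, the FDG-avid and 89Zr-avid "nodes will be determined by 2 board-certified Nuclear Medicine physicians". It gives no criterion for avidity.
- Section 10.2 repeats the timing for the secondary outcome ("Preoperatively, the location and number of" the avid nodes), without mentioning readers.

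Section 12 states that data from both cohorts "will be combined for all primary and secondary analyses". For the primary objective, "we will calculate and compare the sensitivity and specificity of" the two PET tracers; for the secondary, "We will calculate the odds of a false negative using" each tracer. Neither paragraph names the rule that makes a node 89Zr-positive.

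**The concern.** Three candidate rules can be read from the text: the preoperative reader call, 1.4 times mediastinum, and a cut-off adjusted from the ROC curve. (Readers applying 1.4 times would combine the first two.) An analyst could follow the plan as written and report sensitivity at a cut-off chosen after pathology was known, on the nodes being scored. A cut-off picked because it separates these nodes well will look better on them than on new nodes.

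The gain would fall mainly on sensitivity, because positive nodes are few. The secondary outcome, pathology-positive nodes missed by 89Zr, would be understated to match. The comparison with FDG would be asymmetric, since no tuning of an FDG cut-off is described.

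**Working it through.** **1. Inputs from the plan (Section 12, sample size).** 14 subjects × 30 nodes = 420 nodes; prevalence 7.5%; intra-class correlation (ICC) 0.005.
- The plan's own figure reproduces: effective sample size = 420 / (1 + 29 × 0.005) = 420 / 1.145 = 366.8, stated as 367.
- Positive nodes: 420 × 0.075 = 31.5. I used 31 positive and 389 negative.
- The plan gives no figure for ROC optimism, so there is none to reproduce.

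**2. Assumptions not in the documents.** Binormal SUV ratios with equal spread; AUC 0.80, 0.85 and 0.90 in the main runs; an SUV for every node; positives in 7 of the 14 subjects; the ROC-chosen cut-off used in every trial. The last makes the result an upper bound, because the plan adjusts only if needed. The plan does not define its selection criterion precisely, so I ran the two common ones: the Youden index (largest sensitivity + specificity) and the point closest to the top-left corner.

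**3. Optimism.** In each of 4,000 simulated trials per setting, the cut-off was chosen on the 420 nodes. Apparent sensitivity is the value on those nodes. True sensitivity is the value of the same cut-off under the assumed model. Optimism = apparent − true.

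| AUC | Criterion | Apparent | True | Optimism (points) |
|---|---|---|---|---|
| 0.80 | Youden | 0.772 | 0.699 | 7.3 |
| 0.85 | Youden | 0.811 | 0.743 | 6.8 |
| 0.90 | Youden | 0.857 | 0.795 | 6.2 |
| 0.80 | Corner | 0.753 | 0.698 | 5.5 |
| 0.85 | Corner | 0.796 | 0.743 | 5.3 |
| 0.90 | Corner | 0.842 | 0.794 | 4.8 |

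The documents quote an AUC of 0.93 for the fluorescent label on the same antibody. At that value optimism is about 5.6 to 5.8 (Youden) and 4.4 to 4.5 (corner). Specificity optimism is about half a point or less.

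**4. Excess over the ideal cut-off.** With equal spread, the ideal cut-off under either criterion is the midpoint between the two means. Its sensitivity is Φ(Φ⁻¹(AUC)/√2): Φ(0.595) = 0.724, Φ(0.733) = 0.768 and Φ(0.906) = 0.818 at AUC 0.80, 0.85 and 0.90.
- Youden: 0.772 − 0.724 = 4.8 points; 0.811 − 0.768 = 4.3; 0.857 − 0.818 = 3.9.
- Corner: 0.753 − 0.724 = 2.9 points; 0.796 − 0.768 = 2.8; 0.842 − 0.818 = 2.4.

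**5. Missed nodes among 31**, as 31 × (1 − sensitivity), apparent against true:
- Youden: 7.1 against 9.3; 5.9 against 8.0; 4.4 against 6.4.
- Corner: 7.7 against 9.4; 6.3 against 8.0; 4.9 against 6.4.

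**6. Robustness of the sensitivity optimism.**
- ICC 0.1, or positives spread over 14 subjects: 4.9 to 7.4 points.
- SUV spread in one class up to twice the other, within-subject correlation up to 0.2, AUC 0.80 to 0.90: 3.8 to 7.4 points over both criteria.
- Only 39 to 200 benign nodes with an SUV: 4.6 to 7.1 points, and specificity optimism rises to 0.5 to 3.8 points.
- Half the positive nodes without measurable uptake, AUC 0.80 to 0.93: 3.7 to 5.9 points.

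**7. Under the fix.** A rule fixed before pathology has no selection optimism. Leave-one-subject-out selection of the ROC cut-off gave a sensitivity bias between −0.007 and +0.001.

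**The case against.** The strongest reply is that the documents lean towards a fixed call. A node reclassified after pathology was not predicted by the scan, and Section 10.1 has two readers call both tracers before surgery, with pathology then scoring the calls. In Section 12 the ROC step comes under Descriptive statistics, the primary-objective paragraph never refers to it, and its stated use is to judge the tentative cut-off. All of this stands, and it makes the bias conditional. A reader might infer that the plan commits to an ROC-tuned primary result; no passage says so. But the leaning does not close the gap: Section 2.4 places the adjustable cut-off among the outcome measures for the primary and secondary objectives, and no sentence says that the earlier call survives an adjustment.

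A second reply is that this is a 14-subject pilot with no success threshold, and surgeons do not act on the images. With 31 positive nodes the 95% half-width near a sensitivity of 0.75 is 1.96 × √(0.75 × 0.25 / 31) = 0.152, about 15 points before allowing for clustering. That limits the consequences, but a wide interval does not remove a systematic shift, and Section 12 plans tests at the 0.05 level and 95% intervals.

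Three further inferences go too far:
- A reader might reach 8 points by treating 367 as the node count; that gives 8.1 when the ideal sensitivity and specificity are both 0.70. But 367 is a variance adjustment, and the ROC curve would be drawn on the actual nodes.
- A reader might take the 4 to 7 points as the excess over the tracer's best attainable sensitivity. That excess is smaller (step 4). The excess over the 1.4-times rule cannot be computed, because the documents give no distribution of 89Zr uptake in nodes.
- A reader might want an error rate for the test against FDG. The documents give no numeric FDG cut-off and no joint distribution of the two tracers, so only the direction of the asymmetry is claimed.

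Rules for reader disagreement and for FDG positivity would be useful, but the ROC argument does not establish a need for them and they are not part of this point.

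**Conclusion.** The gap in the text is certain: the only numeric 89Zr rule is adjustable after pathology, and nothing states which rule produces the primary and secondary results after that step. The bias is conditional. If a call fixed before pathology governs, it is zero. If the ROC-chosen cut-off is used, reported sensitivity exceeds the true sensitivity of that same cut-off by roughly 4 to 7 points (Youden about 6 to 7, closest-to-corner about 4 to 6) and sensitivity at the ideal cut-off by about 2 to 5. Missed nodes are understated by about 1.5 to 2.2 of 31 (differences in step 5), specificity barely changes, and the comparison with FDG tilts towards 89Zr. These sizes rest on binormal SUV ratios, AUC 0.80 to 0.93, about 31 positive nodes and an SUV for every node. The ambiguity should be removed before the nodes are analysed.

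**What to change.** State in Sections 2.4, 10.1 and 12 that one 89Zr positivity rule, fixed before pathology is known, defines all primary and secondary analyses whatever the ROC curve shows. The sponsor can choose the rule: the preoperative reader call, 1.4 times mediastinum, or readers applying 1.4 times. Report any ROC-chosen cut-off as exploratory only, with its sensitivity and specificity corrected by leave-one-subject-out or a subject-level bootstrap.

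The cost is wording in three sections and a few lines of code. The downside is that, if the locked rule proves a poor cut-off, the primary result may look less favourable, and a better cut-off would have to be confirmed in a later study.
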